7.3.2.17 End of Treatment Visit

- Visit occurs 30 days (+10 days) after the last dose of study drug
- May occur earlier if initiating subsequent antineoplastic therapy
- Assess adverse events

7.3.3 FOLLOW-UP

After the end of treatment assessment, all subjects will be followed with procedures and physical examinations per standard of care.

7.3.4 FINAL STUDY VISIT

When it is determined the study is to be final closed, a Final Study Visit will be performed. This visit will occur at the next regularly scheduled standard of care Follow-Up Visit after trial closure is confirmed. Any AE that is ongoing will be considered ongoing at the Final Study Visit.

Final instructions will be provided to the subject and the subject will be informed if results will be available or any planned presentation or publication of study data.

7.3.5 EARLY TERMINATION VISIT

If a subject terminates study participation for any reason prior to completion of the protocol treatment plan, any subsequent procedures or evaluations will be per physician discretion as part of standard of care. Evaluation of AEs will continue as outlined in Section 7.1.9.

7.3.6 UNSCHEDULED VISIT

Any visit not included on the Schedule of Events Table that includes examination in the Moffitt hematology clinic, inpatient hospitalization or any unexpected extended hospitalization, laboratory

evaluations or management of adverse events, will be considered an **Unscheduled Visit**. It will be documented in the subject’s medical record and included on the adverse event log. Adverse event or serious adverse event data will be collected in Oncore. No separate Oncore form for an unscheduled visit will be used to collect additional data.

7.3.7 SCHEDULE OF EVENTS TABLE

Procedures: Day:	Screening^a	1	2	3	4	5	6	7	10	28	29+ⁱ	End of Treatment/ Early Term.^g	Follow- Up
Informed consent	X												
Demographics and Medical History	X												
Baseline Symptoms ^b		X											
day Performance Status	X												
Concomitant Medication Review	X	Assess throughout Induction and Consolidation											
Review Adverse Events ^c		Assess throughout Induction and Consolidation										X	
CPX-351 Administration ^d		X		X		X							
Physical Examination	X												
Serum pregnancy test ^e	X												
Vital signs (temp, pulse, resp, BP, weight)	X	X		X		X						Per SOC	
Height	X												
12-lead EKG	X												
Echocardiography/MUGA	X										X ^l		
CBC with differential	X	X	X	X	X	X	X	X	X	X	X	Per SOC	
Serum chemistry testing ^f	X	X	X	X	X	X	X	X	X	X	X	Per SOC	
LDH, uric acid, magnesium, phosphorus	X	X	X	X	X	X	X	X				As needed	
Coagulation studies (PT/INR, aPTT, fibrinogen)	X												
Urinalysis with microscopy	X												
Bone marrow biopsy ^k	X										X		
CT or PET/CT Scan ^m	X										X		
Correlative studies ⁿ	X ^{1,2,3}										X ³		
CSF for ALL involvement/IT chemo ^j	X								X				
Follow-Up													X

- a. Screening assessments will be performed within 28 days of the dose of study drug Day 1. Any standard of care procedure performed within 28 days of Day 1, may be used for screening/eligibility even if performed prior to consent.
- b. Baseline symptoms are defined as those present at the closest time before the start of study drug administration.
- c. Adverse event data will be captured from the time of consent until 30 days after the last dose of CPX-351.

- d. CPX-351 induction therapy will only be administered to a subject following hospital admission. One induction will be administered. Patients with a CR, CRi, PR or determined by the PI to be experiencing clinical benefit after induction, may receive up to 3 consolidation treatments, all administered as an outpatient. First consolidation must be administered no earlier than 35-75 days after day 1 of induction. Second and third consolidations will be administered no earlier than 35-56 days after the start of the previous consolidation.
- e. Serum pregnancy test will be performed on females of childbearing potential (FCBP). A FCBP is considered when a sexually mature female: 1) has not undergone a hysterectomy or bilateral oophorectomy; or 2) has not been naturally postmenopausal for at least 12 consecutive months.
- f. Serum chemistry testing will include the following: albumin, BUN, creatinine, alkaline phosphatase, ALT, AST, CO₂, calcium, chloride, glucose, potassium, sodium, total bilirubin, total protein.
- g. The EOT visit will occur 30 days (+10 days) after the last dose of study drug or before the start of subsequent antineoplastic therapy if that occurs sooner.
- h. Correlative studies will be performed as below:
 1. BH3 protein- bone marrow/core biopsy
 2. Ex vivo drug sensitivity assay- bone marrow/core biopsy
 3. T-cell profile- bone marrow/core biopsy/peripheral blood
 4. PDL1 immunohistochemistry- bone marrow/core biopsy
- i. After induction day 28 and through consolidation therapy, laboratory testing will be continued as necessary per standard of care.
- j. Only obtained at screening if symptomatic. Per standard of care, CSF (if no contraindications) will be obtained 7-10 days after initiation of CPX dosing and IT methotrexate will be administered. See Section 7.1.15.
- k. Bone marrow biopsy will be at screening and day 28 of induction therapy. During consolidation therapy, a bone marrow biopsy will be performed on day 28 (+7 days) after the start of each consolidation per standard of care.
- l. Echocardiogram will be repeated for any patient with >550mg/m² daunorubicin (or daunorubicin anthracycline equivalent) exposure. Therapy will only be permitted if the ejection fraction remains >50% and without >10% decrease in ejection fraction from baseline.
- m. CT or PET/CT scan will be utilized at screening and Day 28 as response assessment for subjects with extramedullary disease or for staging purposes as determined by the investigator.

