5 STUDY ENROLLMENT AND WITHDRAWAL

5.1 PARTICIPANT INCLUSION CRITERIA

Patients must meet all of the following criteria to be eligible for study entry:

1. Be willing and able to provide written informed consent/assent for the trial.
2. Be ≥ 18 years of age on day of signing informed consent.
3. Able to adhere to the study visit schedule and other protocol requirements.
4. Pathologically confirmed B- or T-cell acute lymphoblastic or mixed phenotype acute leukemia, with $\geq 5\%$ peripheral blood or bone marrow lymphoblasts and/or extramedullary disease $>1 \times 1 \text{ cm}$.
5. Relapsed or refractory acute lymphoblastic leukemia after at least 1 prior cycle of therapy. Patients with Philadelphia chromosome positive disease must have failed at least two prior tyrosine kinase inhibitors.
6. Eastern Cooperative Oncology Group (ECOG) performance status 0-1.
7. Cardiac ejection fraction $\geq 50\%$ by echocardiography or MUGA.
8. Must be at least 2 weeks out from any prior systemic chemotherapy, blinatumumab, radiation, and/or other investigational agents, and have recovered to grade 1 from any toxicity related to prior therapy. Glucocorticoids are permitted up to 1 day prior to the first dose.
9. Serum bilirubin and creatinine $\leq 1.5 \times$ upper limit of normal (ULN). AST and ALT must be $\leq 3 \times$ ULN, unless there is suspected liver involvement.
10. Females of childbearing potential (FCBP) must have a negative serum pregnancy test at screening. A FCBP is considered when a sexually mature female: 1) has not undergone a hysterectomy or bilateral oophorectomy; or 2) has not been naturally postmenopausal for at least 12 consecutive months.
11. A FCBP must agree to use of two methods of highly effective contraception, be surgically sterile, or abstain from heterosexual activity for the course of the study through 30 days after the last dose of study treatment.
12. Male subjects must agree to use an adequate method of contraception starting with the first dose of study therapy through 30 days after the last dose of study therapy. Men must agree to not donate sperm during and after the study

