7.1.13 Bone Marrow Biopsy

A bone marrow biopsy will be performed at screening and at day 28. If determined the subject has extramedullary disease (as permitted in inclusion criterion #4), biopsy of the involved area will be the method by which correlative samples will be obtained, provided this can be safely obtained. If extramedullary disease is confirmed and the bone marrow biopsy is shown to be negative prior to trial participation, no bone marrow biopsy will be required at day 28. If subject discontinues treatment early or progression of disease is suspected, a bone marrow biopsy will be done at the discretion of the investigator. During follow-up, bone marrow biopsies will be performed per investigator discretion.

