7.3 STUDY SCHEDULE

7.3.1 SCREENING

Screening Visit (Day -28 to -1)

- Obtain and review medical history to determine eligibility based on inclusion/exclusion criteria.

- Written informed consent to be obtained prior to any screening procedures
- Review medications history (including over-the-counter drugs, vitamins, herbs, alcohol) to determine eligibility based on inclusion/exclusion criteria.
- Perform physical examination needed to determine eligibility based on inclusion/exclusion criteria
- Vital signs measurements
- Evaluation of ECOG performance status
- Twelve-lead ECG and Echocardiogram or MUGA.
- Serum beta-human chorionic gonadotropin (β -hCG) pregnancy test for women of childbearing potential
- Clinical laboratory testing including urinalysis, serum chemistry, hematology, and coagulation parameters. Clinical assessments (laboratory tests, ECHO/MUGA, EKG) performed as part of the subject's routine clinical evaluation and not specifically for this study need not be repeated after signed informed consent has been obtained provided the assessments fulfill the study requirements and are performed within 28 days of starting study treatment.
- Bone marrow biopsy and peripheral blood sample will need to be repeated in order to collect correlative samples.
- CT or PET/CT scan of affected areas for subjects determined to have extramedullary disease or for staging purposes prior to treatment.
- Spinal tap if subject is determined to be symptomatic for CNS involvement

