7.3.2 ENROLLMENT/BASELINE/STUDY VISITS

7.3.2.1 Induction Baseline Visit (Day 1)

- In-patient admission
- Verify subject still meets inclusion/exclusion criteria.
- Review results of serum pregnancy test, if applicable.
- Assess and record baseline symptoms prior to study drug administration.
- CBC with differential
- Chemistry profile (ALT, AST, alkaline phosphatase, total bilirubin, calcium, bicarbonate, sodium, potassium, chloride, creatinine, BUN, total protein and albumin)
- LDH, uric acid, magnesium, phosphorus
- Initiation of induction therapy- study drug administration (CPX-351 intravenously)

7.3.2.2 Induction Day 2

- CBC with differential
- Chemistry profile (ALT, AST, alkaline phosphatase, total bilirubin, calcium, bicarbonate, sodium, potassium, chloride, creatinine, BUN, total protein and albumin)
- LDH, uric acid, magnesium, phosphorus

7.3.2.3 Induction Day 3

- CBC with differential
- Chemistry profile (ALT, AST, alkaline phosphatase, total bilirubin, calcium, bicarbonate, sodium, potassium, chloride, creatinine, BUN, total protein and albumin)
- LDH, uric acid, magnesium, phosphorus
- Study drug administration (initiation of CPX-351 intravenously)

7.3.2.4 Induction Day 4

- CBC with differential
- Chemistry profile (ALT, AST, alkaline phosphatase, total bilirubin, calcium, bicarbonate, sodium, potassium, chloride, creatinine, BUN, total protein and albumin)
- LDH, uric acid, magnesium, phosphorus

7.3.2.5 Induction Day 5

- CBC with differential
- Chemistry profile (ALT, AST, alkaline phosphatase, total bilirubin, calcium, bicarbonate, sodium, potassium, chloride, creatinine, BUN, total protein and albumin)
- LDH, uric acid, magnesium, phosphorus
- Study drug administration (initiation of CPX-351 intravenously)

7.3.2.6 Induction Day 6

- CBC with differential
- Chemistry profile (ALT, AST, alkaline phosphatase, total bilirubin, calcium, bicarbonate, sodium, potassium, chloride, creatinine, BUN, total protein and albumin)
- LDH, uric acid, magnesium, phosphorus

7.3.2.7 Induction Day 7

- CBC with differential

- Chemistry profile (ALT, AST, alkaline phosphatase, total bilirubin, calcium, bicarbonate, sodium, potassium, chloride, creatinine, BUN, total protein and albumin)
- LDH, uric acid, magnesium, phosphorus
- Peripheral blood sample for correlative studies
- CSF sample/IT chemo (if no contraindications, will be performed day 7-10 see Section 7.1.15)

7.3.2.8 Induction Day 10

- CBC with differential

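### Disease may be documented up to 28 days before Day 1 while prior systemic therapy need end only 14 days before it, and nothing requires the qualifying or baseline marrow or scan to come after that therapy

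*Combined protocol and SAP*

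**What the plan says.** Screening runs from Day -28 to Day -1 (7.3.1). Footnote a of the Schedule of Events (7.3.7) adds: "Any standard of care procedure performed within 28 days of Day 1, may be used for screening/eligibility even if performed prior to consent".

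Inclusion criterion 8 (5.1) sets the interval from earlier treatment: "Must be at least 2 weeks out from any prior systemic chemotherapy, blinatumumab, radiation, and/or other investigational agents". It also requires recovery of earlier toxicity to grade 1, and then says: "Glucocorticoids are permitted up to 1 day prior to the first dose". Inclusion criterion 4 asks for at least 5% "peripheral blood or bone marrow lymphoblasts and/or extramedullary disease" larger than 1 x 1 cm. It gives no date for that finding relative to the last treatment.

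On repeat sampling, 7.3.1 says: "Bone marrow biopsy and peripheral blood sample will need to be repeated in order to collect correlative samples". On Day 1 (7.3.2.1) staff must "Verify subject still meets inclusion/exclusion criteria"; the tests listed there are blood tests, with no marrow or imaging. In induction, "A bone marrow biopsy will be performed at screening and at day 28" (7.1.13). Extramedullary disease is assessed by CT or PET/CT at baseline and Day 28 (7.1.16).

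**The concern.** The look-back for eligibility evidence is longer than the required interval since systemic therapy. A patient could have a marrow with blasts on Day -28, receive another regimen that ends on Day -14, and start CPX-351 on Day 1, with the stated time limits all met. If that regimen cleared the marrow, the Day 28 marrow would find under 5% blasts whether or not CPX-351 did anything.

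The primary endpoint is CR/CRi at Day 28 (4.2.1) in a single-arm study, so there is no concurrent group in which the same carry-over would show. The count also feeds the rule in 10.4.1 that 4 or more CR/CRi in the first 10 patients leads the company to consider funding 9 more. With ten patients, one misattributed response moves the observed rate by 10 percentage points. Partial response in Appendix A also depends on the baseline, since it uses a fall in blasts of more than 50%.

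**Working it through.** **Timing**

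- Oldest eligibility evidence: 28 days before Day 1 (7.3.1; 7.3.7 footnote a).
- Shortest interval since systemic chemotherapy, blinatumomab or an investigational agent: 14 days (criterion 8).
- Shortest interval since glucocorticoids: 1 day (criterion 8; 7.6).
- Overlap for systemic therapy: 28 - 14 = 14 days.
- Overlap for glucocorticoids: 28 - 1 = 27 days.
- Radiation: criterion 8 says two weeks, but exclusion 2 bars it within four weeks. 28 - 28 = 0 days, so radiation adds no gap.

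**Does another provision close the overlap?**

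- *Repeat marrow (7.3.1).* It is required, but its stated purpose is correlative sampling. It falls in the same 28-day window, is not placed after the last treatment, and is not named as the qualifying or baseline sample.
- *Day 1 check (7.3.2.1).* A blood count can show that circulating blasts have gone. It cannot show whether marrow blasts are still at least 5%.
- *Extramedullary disease.* The baseline scan has the same window, and no repeat scan is required before Day 1.
- *Ban on other anti-cancer treatment (7.6).* It covers the treatment phase only, not screening.

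**The plan's own figures**

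The illustrative Simon row in 10.4.2 has n1 = 10, r1 = 3, N = 19, R = 9. At a rate of 0.35:

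- P(X <= 3 | 10, 0.35) = 0.0135 + 0.0725 + 0.1757 + 0.2522 = 0.514, the printed probability of early termination.
- Average N = 10 + (1 - 0.5138) x 9 = 14.38, as printed.
- Exact two-stage alpha is 0.084, and beta at 0.65 is 0.095; both are as printed.

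The chance of reaching 4 of 10 at a true 35% is therefore 1 - 0.5138 = 48.6%.

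**Illustration of carry-over**

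The documents give no frequency of carried-over remission. Both settings below are assumptions, and each treats a carried-over patient as certain to be scored CR/CRi.

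(a) A fraction q of patients carries over a remission. The apparent rate is p = q + (1 - q) x 0.35.

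| q | p | P(X >= 4 of 10) |
|---|---|---|
| 0 | 0.350 | 48.6% |
| 2% | 0.363 | 52.1% |
| 5% | 0.3825 | 57.3% |

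(b) Exactly k of the ten carry over a remission. The rule is met if the other 10 - k patients supply at least 4 - k responses at 35%. The expected observed rate is (k + (10 - k) x 0.35) / 10.

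| k | Expression | P(rule met) | Expected observed rate |
|---|---|---|---|
| 0 | P(X >= 4 of 10) | 48.6% | 35.0% |
| 1 | P(X >= 3 of 9) | 66.3% | 41.5% |
| 2 | P(X >= 2 of 8) | 83.1% | 48.0% |

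**The case against.** The strongest reply is that several provisions already work against this sequence.

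- Section 7.3.1 lists laboratory tests, ECHO/MUGA and EKG as the assessments that need not be repeated after consent, and then says the marrow must be repeated. For marrow patients the specific text arguably overrides footnote a. The repeat marrow must also supply fresh leukemia cells for the ex vivo assay (7.2.2, 13.4.1).
- Exclusion 4 lets the investigator bar a patient whose therapy might confound the results, and eligibility is checked again on Day 1.
- A patient already cleared may no longer meet criteria 4 and 5, and recovery of toxicity to grade 1 takes time after intensive treatment.
- Medications within 30 days of screening are recorded (7.4), and baseline blast burden and response to prior therapies are summarized (10.4.6), so intervening therapy can be traced.
- CR needs more than under 5% blasts: Appendix A adds absence of extramedullary disease, count recovery and red-cell transfusion independence, with CRi relaxing only neutrophils or platelets.

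Most of this stands, and it makes the sequence narrower than the dates alone suggest. It does not remove it. Exclusion 4 is a matter of opinion. Whether criterion 4 still holds on Day 1 cannot be judged without a marrow or scan. The repeat marrow can itself precede the last treatment, or follow it without being used as the baseline. The medication record shows that therapy was given, not what the marrow looked like afterwards.

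A reader might infer that the plan has no safeguard, or that it will credit earlier regimens' remissions to CPX-351. The documents support neither: safeguards exist, and no frequency is given.

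**Conclusion.** The gap is real but bounded. The timing rules permit disease documentation that precedes the end of prior systemic therapy by up to 14 days, or the end of glucocorticoids by up to 27 days, and no provision ties the baseline to the last treatment. A remission from earlier therapy could then enter the CR/CRi count.

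The overlap in days follows directly from the text. The probabilities do not: they rest on an assumed carry-over frequency and on certain scoring as CR/CRi. Under those assumptions the chance of meeting the 4-of-10 rule at a true 35% moves from 48.6% to about 52% to 57% for a carry-over fraction of 2% to 5%, 66.3% for one patient in ten and 83.1% for two.

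A reader might also infer that a formal type I error is compromised. That goes too far. All endpoints are exploratory (10.2, 10.4.11), the Simon table is offered for illustration only (10.4.2), and reaching 4 of 10 leads only to consideration of more budget (10.4.1). What is affected is the CR/CRi estimate and that trigger. This should be fixed, but it does not invalidate the pilot.

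**What to change.** In inclusion criterion 4 and footnote a of 7.3.7, state that the marrow, blood or imaging that documents disease and serves as the response baseline must be obtained after the last dose of prior systemic chemotherapy, blinatumomab or investigational agent. Name the repeat screening marrow already required in 7.3.1 as that sample for marrow patients.

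Do not apply this timing rule to glucocorticoids. Since they may continue to the day before dosing, it would force a marrow at about Day -1. Instead, use the medications already recorded to report CR/CRi with and without patients given glucocorticoids after the baseline marrow.

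This governs when data are collected and changes no treatment or washout rule. It needs a short amendment and one extra tabulation. The downside is that an older outside marrow or scan would no longer qualify a patient on its own, and a few patients may need a newer scan or a later-timed marrow. For most marrow patients no procedure is added. The rule has to be in place before dosing, because disease status before CPX-351 cannot be recovered afterwards.

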7.4 CONCOMITANT MEDICATIONS, TREATMENTS, AND PROCEDURES

All subjects should be maintained on the same medications throughout the study period, as medically feasible.

The investigator should instruct the subject to notify the study staff about any new medications he/she takes after the start of the study drug. All medications (other than study drug) and significant non-drug therapies (including physical therapy and blood transfusions) administered after the subject starts treatment with study drug must be recorded:

- Administration of pegfilgrastim or filgrastim following initiation of protocol therapy will occur for all patients. It is suggested dosing start at Day 6.
- Administration of erythropoietin or darbopoietin is allowed;
- Patients must be instructed not to take any additional medications (including herbal supplements and over-the-counter products) during the trial without prior consultation with the investigator. All medications taken within 30 days of screening should be recorded. If concomitant therapy must be added or changed, the reason and name of the drug/therapy should be recorded;
- In general, the use of any concomitant medication/therapies deemed necessary for the care of the patient are allowed, including drugs given prophylactically (e.g. antiemetics).

7.5 JUSTIFICATION FOR SENSITIVE PROCEDURES

7.5.1 PRECAUTIONARY MEDICATIONS, TREATMENTS, AND PROCEDURES

- Subjects will not routinely be pre-medicated for hypersensitivity or infusion-related reactions initially during the first infusion of the first treatment course. If a reaction occurs, pre-medications for subsequent infusions will be at investigator discretion. Infusion reactions will be treated per Moffitt institutional standards.
- In previous clinical trials, no drug or food interactions were identified as being associated with CPX-351.

7.6 PROHIBITED MEDICATIONS, TREATMENTS, AND PROCEDURES

- An evaluation of prior exposure to anthracyclines should be performed during screening. Per the study Exclusion Criteria, subjects with prior cumulative anthracycline exposure of greater than 368 mg/m² daunorubicin will be excluded.
- High dose corticosteroids used for management of ALL symptoms are permitted up to one day prior to the first dose of study drug. Corticosteroids required as pre-medication for CT scans or for short-term use as treatment for adverse events, are permitted in consultation with the PI.
- Other anti-cancer treatment is not permitted during the treatment phase of the study.

